DMC	Data Monitoring Committee
ECG	Electrocardiogram
FDA	Food and Drug Administration
FDA	Food and Drug Administration
FEV	forced expiratory volume
FIH	first in human
FVC	forced vital capacity
GCP	Good Clinical Practice
GINA	Global Initiative for Asthma

GLP	Good Laboratory Practice
h	hour
HIV	human immunodeficiency virus
hPaSMc	human pulmonary artery smooth muscle cell
HR	heart rate
HV	healthy volunteer
Hx/Su	Hypoxia/Sugen
i.t.	intra-tracheal
i.v.	intravenous
ICH	International Conference on Harmonization of Technical Requirements for Registration of Pharmaceuticals for Human Use
IEC	Independent Ethics Committee
IPR	prostacyclin receptor
IRB	Institutional Review Board
IRT	Interactive Response Technology
LDH	lactate dehydrogenase
LLOQ	lower limit of quantification
LV	left ventricular
MAD	multiple ascending dose
MCT	monocrotaline
mg	milligram(s)
mL	milliliter(s)
mPAP	mean pulmonary artery pressure
MTD	maximum tolerated dose
NOAEL	no observed adverse effect level
NT-proBNP	N-terminal prohormone of brain natriuretic peptide
NYHA	New York Heart Association
PA	pulmonary artery
PAH	pulmonary arterial hypertension
PCWP	Pulmonary Capillary Wedge Pressure
PD	pharmacodynamic(s)
PG	pharmacogenetic

PH	pulmonary hypertension
PK	pharmacokinetic(s)
PVR	pulmonary vascular resistance
RA	right atrium
REB	Research Ethics Board
RHC	right heart catheterization
RV	right ventricular
SAD	single ascending dose
SAE	serious adverse event
SAP	Statistical Analysis Plan
SD	standard deviation
SOM	Site Operations Manual
SUSAR	Suspected Unexpected Serious Adverse Reactions
TBL	total bilirubin
ULN	upper limit of normal
WHO	World Health Organization

Pharmacokinetic definitions and symbols

Ae0-t	Amount of drug (or defined metabolite) excreted into the urine from time zero to time 't' where t is a defined time point after administration [mass units or % of dose]
AUC0-t	The area under the plasma (or serum or blood) concentration-time curve from time zero to time 't' where t is a defined time point after administration [mass x time / volume]
AUCinf	The area under the plasma (or serum or blood) concentration-time curve from time zero to infinity [mass x time / volume]
AUClast	The area under the plasma (or serum or blood) concentration-time curve from time zero to the time of the last quantifiable concentration [mass x time / volume]
AUCtau	The area under the plasma (or serum or blood) concentration-time curve from time zero to the end of the dosing interval tau [mass x time / volume]
AUCtau,ss	The area under the plasma (or serum or blood) concentration-time curve from time zero to the end of the dosing interval tau at steady state [mass x time / volume]
Cav,ss	The average steady state plasma (or serum or blood) concentration during multiple dosing
CL	The systemic (or total body) clearance from plasma (or serum or blood) following intravenous administration [volume / time]
CL/F	The apparent systemic (or total body) clearance from plasma (or serum or blood) following extravascular administration [volume / time]
CLr	The renal clearance from plasma (or serum or blood) [volume / time]
Cmax	The observed maximum plasma (or serum or blood) concentration following drug administration [mass / volume]
Cmax,ss	The observed maximum plasma (or serum or blood) concentration following drug administration at steady state [mass / volume]
Cmin,ss	The lowest plasma (or serum or blood) concentration observed during a dosing interval at steady state [mass / volume]
F	Bioavailability of a compound. Fabs is the absolute bioavailability, i.e. the fraction (or percentage) of the administered extravascular dose systemically available. Frel is the relative bioavailability, i.e. the bioavailability relative to a reference
MRT	Mean residence time determined as $AUMC_{inf}/AUC_{inf}$ following intravenous administration [time]
Racc	The accumulation ratio
T1/2	The terminal elimination half-life [time]

T _{1/2,acc}	The effective half-life based on drug accumulation at steady state [time]
T _{max}	The time to reach the maximum concentration after drug administration [time]
V _{ss}	The volume of distribution at steady state following intravenous administration [volume]
V _z	The volume of distribution during the terminal elimination phase following intravenous administration [volume]
V _{z/F}	The apparent volume of distribution during the terminal elimination phase following extravascular administration [volume]

Glossary of terms

Assessment	A procedure used to generate data required by the study
Cohort	A specific group of subjects fulfilling certain criteria
Control drug	Any drug (an active drug or an inactive drug, such as a placebo) which is used as a comparator to the investigational drug being tested in the trial
Dosage	Dose of the study treatment given to the subject in a time unit (e.g. 100 mg once a day, 75 mg twice a day)
Enrollment	Point/time of subject entry into the study at which informed consent must be obtained (i.e. prior to starting any of the procedures described in the protocol)
Epoch	Interval of time in the planned conduct of a study. An epoch is associated with a purpose (e.g. screening, randomization, treatment, follow-up), which applies across all arms of a study.
Healthy volunteer	A person with no known significant health problems who volunteers to be a study participant
Investigational drug	The study drug whose properties are being tested in the study; this definition is consistent with US CFR 21 Section 312.3 and Directive 2001/20/EC and is synonymous with “investigational new drug” or “test substance”
Investigational treatment	All investigational drug(s) whose properties are being tested in the study as well as their associated treatment controls. This includes any placebos, any active controls, as well as approved drugs used outside of their indication/approved dosage or tested in a fixed combination. Investigational treatment generally does not include other treatments administered as concomitant background therapy required or allowed by the protocol when used within approved indication/dosage.
Medication number	A unique identifier on the label of each study drug package in studies that dispense study drug using an IRT system.
Medication pack number	A unique identifier on the label of each drug package in studies that dispense study treatment using an IRT system
Non-investigational medicinal Product (NIMP)	Products which are not the object of investigation (e.g. any background therapy administered to each of the clinical trial subjects, regardless of randomization group, rescue medication, active drug run-ins etc.)
Part	A single component of a study which contains different objectives or populations within that single study. Common parts within a study are: a single dose part and a multiple dose part, or a part in patients with established disease and in those with newly-diagnosed disease.
Patient	An individual with the condition of interest

Period	A minor subdivision of the study timeline; divides phases into smaller functional segments such as screening, baseline, titration, washout, etc.
Premature subject withdrawal	Point/time when the subject exits from the study prior to the planned completion of all study drug administration and assessments; at this time all study drug administration is discontinued and no further assessments are planned.
Randomization number	A unique identifier assigned to each randomized subject, corresponding to a specific treatment arm assignment
Screen Failure	A subject who is screened but is not treated or randomized
Stage	A major subdivision of the study timeline; begins and ends with major study milestones such as enrollment, randomization, completion of treatment, etc.
Study completion	Point/time at which the subject came in for a final evaluation visit or when study drug was discontinued whichever is later.
Study drug discontinuation	Point/time when subject permanently stops taking study drug for any reason; may or may not also be the point/time of premature subject withdrawal.
Study drug/treatment	Any drug (or combination of drugs) administered to the subject as part of the required study procedures; includes investigational drug, active drug run-ins or background therapy.
Study treatment	Any drug administered to the study participants as part of the required study procedures; includes investigational drug (s), control(s) or non-investigational medicinal product(s)
Study treatment discontinuation	When the subject permanently stops taking study treatment prior to the defined study treatment completion date
Subject	A trial participant (can be a healthy volunteer or a patient)
Subject number	A unique number assigned to each subject upon signing the informed consent. This number is the definitive, unique identifier for the subject and should be used to identify the subject throughout the study for all data collected, sample labels, etc.
Treatment number	A unique identifier assigned in non-randomized studies to each dosed subject, corresponding to a specific treatment arm
Variable	A measured value or assessed response that is determined in specific assessments and used in data analysis to evaluate the drug being tested in the study
Withdrawal of consent (WoC)	Withdrawal of consent from the study is defined as when a subject does not want to participate in the study any longer, and does not want any further visits or assessments, and does not want any further study related contact, and does not allow analysis of already obtained biologic material

Corporate Confidential Information

Protocol synopsis

Protocol number	CQCC374X2201E1
Title	Long-term, open label, multicenter, extension study to evaluate the safety and tolerability of QCC374 in patients with pulmonary arterial hypertension (PAH)
Brief title	Long-term extension study of the safety and pharmacokinetics of QCC374 in PAH patients
Sponsor and Clinical Trial Phase	Novartis Phase 2 (Extension Study)
Intervention type	Drug
Study type	Interventional
Purpose and rationale	The purpose of this study, as a long-term open-label safety extension to the Phase 2a study of inhaled QCC374 in adult patients with PAH, is to provide patients with the option to continue receiving QCC374 after completion of the QCC374X2201 trial, and monitor the long-term safety, tolerability and efficacy of QCC374 in patients with PAH.
Primary Objective(s)	To evaluate the safety and tolerability of QCC374 in patients with PAH over a two year period
Secondary Objectives	
 • To assess the treatment effect of QCC374 in PAH patients not previously dosed with QCC374 (i.e., those subjects previously in the placebo group of QCC374X2201, Arm 2) 
 • Six Minute Walk Distance (6MWD) • Right Ventricular (RV) function with echocardiography • To evaluate the pharmacokinetics of QCC374 and its metabolite QCM441 in PAH patients not previously dosed with QCC374 (i.e., subjects previously in the placebo group of QCC374X2201, Arm 2)
Study design	
This is a multicenter, open label trial to assess the safety, tolerability pharmacokinetics and efficacy of inhaled QCC374 over a two year period in patients with PAH who have completed study QCC374X2201. This study will have two arms. In Arm 1, patients who had been randomized to active in the QCC374X2201 study will continue on QCC374 at their highest stable dose. In Arm 2, the patients who had been randomized to placebo will complete a titration scheme similar to that of the active arm in QCC374X2201 protocol.
 
For both arms the study consists of a screening visit, a treatment period of 720 days, and an EOS visit 30 days after treatment is completed. This study may be amended in the future to increase the treatment duration period, as additional data emerges for QCC374 in PAH.
 
All patients willing to participate in this trial will roll-over directly from the QCC374X2201 study after their 112 days of participation has been completed. The electrocardiogram (ECG), pulse oximetry, vital signs, weight, spirometry, 6MWD, Corporate Confidential Information hematology, blood chemistry, body measurement and urinalysis results from the QCC374X2201 Visit Day 111 visit will be used as the baseline assessments for the extension study.

Population	The study population will be comprised of male and female PAH patients who have completed the QCC374X2201 PoC study and wish to participate in the extension study. A total of approximately 38 subjects are planned to be enrolled and randomized in the QCC374X2201 study, with approximately 30 patients expected to complete the study.
Key Inclusion criteria	
 • Written informed consent must be obtained before any assessment is performed. • Subject was enrolled in the QCC374X2201 study and completed per protocol
Key Exclusion criteria	
 • Subjects who have started receiving prostacyclin (epoprostenol), prostacyclin analogs (i.e. trepostinil, iloprost, beraprost) or prostacyclin receptor agonists (i.e. selexipag) since the last study drug intake in the QCC374X2201 study. • Females who are pregnant, or who plan to become pregnant during the study, or who are breastfeeding • Any known factor or disease that may interfere with treatment compliance or study conduct (i.e. drug or alcohol dependence) • Subjects who withdrew consent from the study QCC374X2201
Study treatment	
 • QCC374 0.015 mg • QCC374 0.06 mg
Efficacy/PD assessments	
 • 6MWD • RV function with echocardiography
Key safety assessments	
 • Adverse event (AE) monitoring • Physical examinations • Spirometry • ECG • Blood Chemistries, Hematology and Urinalysis
Other assessments	
Corporate Confidential Information
 
 • PK - in those subjects who had not previously received QCC374 in the QCC374X2201 trial 
Corporate Confidential Information

Data analysis	
All data for vital signs, ECG evaluations and clinical laboratory evaluations will be listed by subject and visit/time and summarized by descriptive statistics. All information obtained on AEs will be displayed by subject. The number and percentage of subjects with AEs will be tabulated by body system and preferred term and QCC374X2201 study treatment group (QCC374 or placebo). A subject with multiple AEs within a body system is only counted once towards the total of this body system.
 
Baseline and end of study assessments from QCC374X2201 study will be included in the summary tables. Summary statistics will be presented by QCC374X2201 study treatment group.
 
No inferential statistical analysis will be performed.

Key words	Pulmonary Arterial Hypertension

1 Introduction

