3.1 Study design

This is a multicenter, open label trial to assess the safety, tolerability, pharmacokinetics and efficacy of inhaled QCC374 over a two year period, in subjects with PAH who have completed study QCC374X2201. This study will have two arms (Figure 3-1). In Arm 1, subjects randomized to active in the QCC374X2201 study will continue on QCC374 at their highest stable dose. In Arm 2, the subjects randomized to placebo in the QCC374X2201 study will complete a titration scheme similar to that of the active arm in QCC374X2201 protocol. For subjects in both Arms, the assessments obtained during the Day 111 visit for the companion QCC374X2201 study (including physical examination, vital signs, pulse oximetry, ECG, spirometry, 6MWD, **Corporate Confidential** and laboratory data) will be used as the baseline values for this study. **Information**

[figure not shown]
This study may be amended in the future to increase the treatment duration period, as additional data emerges for QCC374 in PAH.

Figure 3-1 QCC374X2201E1 Extension Study Design

Arm 1

Arm 2

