Alcoholic hepatitis	
• Ethanol history, gGT, MCV, CD-transferrin
Nonalcoholic steatohepatitis	
• Ultrasound or MRI
Hypoxic/ischemic hepatopathy	
• Medical history: acute or chronic CHF, hypotension, hypoxia, hepatic venous occlusion. Ultrasound or MRI.
Biliary tract disease	
• Ultrasound or MRI, ERCP as appropriate.
Wilson disease	
• Caeruloplasmin
Hemochromatosis	
• Ferritin, transferrin
Alpha-1-antitrypsin deficiency	
• Alpha-1-antitrypsin

16 Appendix 2: Specific Renal Alert Criteria and Actions

Table 16-1 Specific Renal Alert Criteria and Actions

Criteria	Action required
Serum creatinine (sCr) increase 25 – 49% compared to baseline	
 Consider causes and possible interventions Follow up within 2-5 days
Serum creatinine increase $\geq 50\%$	
 Consider causes and possible interventions Repeat assessment within 24-48h if possible Consider drug interruption or discontinuation unless other causes are diagnosed and corrected Consider hospitalization and specialized treatment
Protein-creatinine or albumin-creatinine ratio increase ≥ 2 -fold or new onset dipstick proteinuria $\geq 1+$ or Albumin-creatinine ratio (ACR) ≥ 30 mg/g or ≥ 3 mg/mmol; or Protein-creatinine ratio (PCR) ≥ 150 mg/g or >15 mg/mmol	
 Consider causes and possible interventions Assess serum albumin & serum protein Repeat assessment to confirm Consider drug interruption or discontinuation unless other causes are diagnosed and corrected
New onset glucosuria on urine dipstick (unless related to concomitant treatment, diabetes)	
Assess & document:
 
 Blood glucose (fasting) Serum creatinine Urine albumin-creatinine ratio
New hematuria on dipstick	
Assess & document:
 
 Urine sediment microscopy Assess sCr and urine albumin-creatinine ratio Exclude infection, trauma, bleeding from the distal urinary tract/bladder, menstruation Consider bleeding disorder

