Additional specialized assessments are available to assess renal function or renal pathology. (Note: In exceptional cases when a nephrologist considers a renal biopsy, it is strongly recommended to make specimen slides available for evaluation by Novartis to potentially identify project-wide patterns of nephrotoxicity.)

Whenever a renal event is identified, a detailed subject history and examination are indicated to identify, document and potentially eliminate risk factors that may have initiated or contributed to the event:

- Blood pressure assessment (after 5 min rest, with an appropriate cuff size)
- Signs and symptoms such as fever, headache, shortness of breath, back or abdominal pain, dysuria, hematuria, dependent or periorbital edema
- Changes in blood pressure, body weight, fluid intake, voiding pattern, or urine output
- Concomitant events or procedures such as trauma, surgical procedures, cardiac or hepatic failure, contrast media or other known nephrotoxin administration, or other potential causes of renal dysfunction, e.g., dehydration, hemorrhage, tumor lysis

Table 16-2 Follow-up of renal events

Action	Follow up
Assess*, document and record in the Case Report Form (CRF) or via electronic data load. Review and record possible contributing factors to the renal event (co-medications, other co-morbid conditions) and additional diagnostic procedures (MRI etc) in the CRF.	
 • Urine dipstick and sediment microscopy • Blood pressure and body weight • Serum creatinine, electrolytes (sodium, potassium, phosphate, calcium), bicarbonate and uric acid • Urine output
Monitor subject regularly (frequency at investigator's discretion) until:	
 • Event resolution: (sCr within 10% of baseline or protein-creatinine ratio within 50% of baseline) 
or
 
 • Event stabilization: sCr level with $\pm 10\%$ variability over last 6 months or protein-creatinine ratio stabilization at a new level with $\pm 50\%$ variability over last 6 months.

* Urine osmolality: in the absence of diuretics or chronic kidney disease this can be a very sensitive metric for integrated kidney function that requires excellent tubular function. A high urinary osmolality in the setting of an increase in sCr will point toward a “pre-renal” cause rather than tubular toxicity.

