6.1.1 Variables

The secondary variables are:

- 6MWD
- Right ventricular (RV) function with echocardiography, measured at baseline and at 16 weeks. See Table 6.1 for details.

Table 6-1 Imaging parameters (secondary endpoints)

Imaging parameter (name as in the dataset)	Description	Unit	Directionality
Tvsa	Tricuspid annular peak systolic velocity	cm/sec	Higher is better
tei_index	RV Tei Index	Unitless	Lower is better
Rvfac	RV fractional area change	%	Higher is better
Rvfwls	RV free wall average peak longitudinal strain	%	Lower is better
Tapse	Tricuspid annular plane systolic excursion	cm	Higher is better

The following two definitions of baseline will be used, and where change from baseline will be reported both definitions will be used:

1. Core: Baseline is defined as the Core study (QCC374X2201) baseline visit.
2. Extension: Baseline will be defined as the Extension study (QCC374X2201E1) baseline. The Extension baseline is defined as the Day 112 of the Core study.

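### In Arm 1 the percent-creatinine alerts restart from an on-QCC374 value, so a rise accumulated over both studies can pass without an extension alert, and the SAP reports no laboratory change from the pre-drug baseline

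*Protocol*

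**What the plan says.** **Baseline.** The synopsis provides that "blood chemistry, body measurement and urinalysis results from the QCC374X2201 Visit Day 111 visit will be used as the baseline assessments" for the extension. Protocol section 3.1 repeats the rule: "For subjects in both Arms, the assessments obtained during the Day 111 visit for the companion QCC374X2201 study", laboratory data included, serve as this study's baseline values.

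**Prior exposure.** The two arms reach that visit differently. "In Arm 1, subjects randomized to active in the QCC374X2201 study will continue on QCC374 at their highest stable dose", whereas Arm 2 took placebo in Core and starts QCC374 on extension Day 1. Subjects "will roll-over directly from the QCC374X2201 study after their 112 days of participation has been completed". In Arm 2, footnote 7 of Table 8-2 has the laboratory tests repeated before dosing if the Day 111 results are more than 4 days old.

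**Alerts.** The first row of Table 16-1 (Appendix 2) is "Serum creatinine (sCr) increase 25 – 49% compared to baseline". The next row is a rise of at least 50%, with the reference not restated. Other rows depend on a new dipstick finding or a doubling of a urine protein ratio. Table 16-2 treats a renal event as resolved with "sCr within 10% of baseline or protein-creatinine ratio within 50% of baseline". Appendix 2 does not say which baseline it means, and it has no provision for events carried over from Core.

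**Analysis.** SAP 6.1.1 uses two baselines wherever change in the secondary variables is reported. One is the pre-treatment value: "Core: Baseline is defined as the Core study (QCC374X2201) baseline visit". The other is the extension baseline, given as Core Day 112. SAP 7.2 presents baseline characteristics at both and defines a spirometry baseline by arm. For laboratory data it plans listings, normal-range flags and summaries by arm and visit, with no baseline and no change from baseline.

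**The concern.** Safety over two years is the primary objective, and Arm 1 is the longest-exposed group. A percent-change trigger detects a drug-related drift only if its reference predates the drug. Followed as written, the same table judges Arm 2 against a value before QCC374 and Arm 1 against a value on it. A rise that began in Core disappears from the Arm 1 reference, and two successive sub-threshold rises need never trigger the rule.

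Little elsewhere would bring the cumulative change to light for an individual. The eligibility criteria (4.1, 4.2) contain no renal criterion, so a subject with raised creatinine can enter. The extension has no data monitoring committee (10.4). The planned laboratory summaries are at group level and do not show one subject's change from before treatment.

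**Working it through.** The documents state no sample size, power or event rate for this point, so there is no planned figure to reproduce. The check is ratio arithmetic.

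**Inputs**
- Extension baseline: Core Day 111 (synopsis; section 3.1). 111/7 = 15.9 weeks; 112/7 = 16.0 weeks.
- Alert thresholds: +25% and +50% (Table 16-1). I take the 50% row to use the same reference as the row above it.
- Resolution band: within 10% of baseline (Table 16-2).
- r = fractional creatinine change in Arm 1 from the Core pre-drug baseline to Day 111. **The documents give no value, so r is an assumption and is shown as a range.**

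**Formulas**
- An extension alert set at a fires when creatinine exceeds the pre-drug value by (1 + r)(1 + a) − 1.
- The upper edge of the resolution band, over the pre-drug value, is (1 + r)(1.10) − 1.

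| r (assumed) | 25% alert fires at | 50% alert fires at | Upper edge of resolution band |
|---|---|---|---|
| 0% | +25% | +50% | +10% |
| 10% | +37.5% | +65% | +21% |
| 20% | +50% | +80% | +32% |
| 24% | +55% | +86% | +36.4% |
| 30% | +62.5% | +95% | +43% |
| 50% | +87.5% | +125% | +65% |

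All entries are relative to the pre-drug value. With the Core baseline as reference, every row would equal the first.

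**Cumulative rises with no extension percent-change alert**
- 12% then 12%: 1.12 × 1.12 = 1.254, or +25%.
- 20% then 24%: 1.20 × 1.24 = 1.488, or +49%.
- 24% then 24%: 1.24 × 1.24 = 1.538, or +54%.

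After a 24% rise in Core, a further 1.50/1.24 − 1 = 21% brings the total to +50%, which is still below the 25% extension trigger. Whether the Core part of these rises would have raised an alert in Core depends on thresholds that the documents do not give.

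**Direction.** If creatinine fell in Core, the effect reverses. With r = −10%, the 25% alert fires at 0.90 × 1.25 = 1.125, only 12.5% above the pre-drug value.

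**Carried-over elevation.** Whatever r is, the Day 111 value divided by itself is 1, a change of 0%. It lies inside the 10% band by construction if Table 16-2 and the extension baseline are applied to it. No passage says whether they are.

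**The case against.** The strongest reply is that Table 16-1 is one safeguard among several, and that much stands.

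- Protocol 8.6.6 requires clinically relevant laboratory deviations to be reported to the sponsor and repeated until they normalize or cease to matter clinically.
- Section 9.1 has investigators review values outside normal ranges and follow adverse events until they resolve or are judged permanent.
- Section 11.4.4 and SAP 7.2 flag values against normal ranges.
- The absolute urine albumin and protein ratio limits in Table 16-1 need no baseline.

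What can be missed is therefore a percent-change trigger, not necessarily the rise itself. These safeguards do not fully close the gap. The 8.6.6 rule is a judgement with no named reference. Section 9.1 also invokes change from baseline. The only renal definition of resolution is in Table 16-2.

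A second reply is that section 11.4.2 already brings Core baseline assessments into the summary tables. It does, at group level; it does not show cumulative change by subject.

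Two stronger readings are tempting, and the documents do not support them.

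- A reader might infer that an unresolved renal event from Core counts as resolved on entry. The protocol does not say so. This follows only if Table 16-2 and the extension baseline are applied to an event opened under another protocol, which is not available here.
- A reader might infer that the comparison is biased in favour of Arm 1. That requires creatinine to have risen in Core, which is unknown. The SAP also plans no tabulation of renal alerts by arm and no inferential analysis.

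**Conclusion.** The point holds as a defect of reference, with mitigation. On the plain reading of the synopsis and section 3.1 with Appendix 2, the Arm 1 creatinine alerts are measured from a value after about 16 weeks on QCC374, and those of Arm 2 from a value before it. The percent-change alerts therefore do not mean the same thing in the two arms, whichever way creatinine moved in Core.

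The size depends wholly on the unknown change in Core. For assumed rises of 10% to 30%, the 25% alert moves to between +37.5% and +62.5% over the pre-drug value. With no Core change there is no effect.

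The handling of renal events ongoing from Core is a gap in the text, not a stated rule. Separately, the protocol and SAP disagree on the day: the protocol uses Core Day 111, while SAP 1.4 and 6.1.1 use Day 112. The laboratory reporting should be changed, because these data belong to the primary objective and the SAP already applies the two-baseline approach to secondary variables.

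**What to change.** **SAP 7.2, clinical laboratory evaluations.** Define both baselines for laboratory data. For Arm 1, report change in creatinine and the other laboratory parameters from the Core (pre-QCC374) baseline alongside the extension baseline. Add a subject-level listing that flags values meeting the percent-change rows of Table 16-1 against each baseline. This extends the approach of SAP 6.1.1 to primary safety data. It is a reporting change only: it makes cumulative rises visible in the analysis and does not alter what sites do during the study.

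**Protocol.** The sponsor should reconcile the synopsis and section 3.1 with Appendix 2 by stating which value is meant by baseline, and by a new-onset finding, for Arm 1 and for renal events ongoing from Core. No threshold, closure rule or clinical action is proposed here.

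**Both documents.** Reconcile Core Day 111 (protocol) with Core Day 112 (SAP 1.4 and 6.1.1).

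**Cost.** Wording in the SAP and Appendix 2, and minor programming. No new measurements should be needed, since section 11.4.2 already has Core baseline assessments feeding the summary tables. The downside is a few more flags in Arm 1.
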